In healthy subjects, lenalidomide was rapidly absorbed following single- and multiple-dose oral administration, with the maximum concentration (C_{max}) occurring between 0.5 and 1.5 hours postdose. The C_{max} and area under the concentration-time curve (AUC) values increased proportionally from 5 to 400 mg/day in single-dose studies. Steady-state levels were observed within 4 days of multiple dosing. There was no accumulation of drug with multiple dosing. Coadministration with food delayed absorption somewhat, but did not alter the extent of absorption.

Approximately, 65% to 85% of lenalidomide was eliminated unchanged through urinary excretion. The mean renal clearance of lenalidomide was approximately 180 to 220 mL/min across all doses, which exceeded the glomerular filtration rate, and therefore is at least partially active. The mean total clearance of lenalidomide was approximately 300 mL/min, and it was independent of time and dose. The mean half-life of elimination ($t_{1/2}$) was approximately 3 to 4 hours on all study days at the clinically relevant doses (5 to 50 mg/day).

Following a single 25-mg dose of [14C]-lenalidomide as an oral suspension, total recovery of urinary radioactivity indicated that approximately 90% of the administered dose was absorbed systemically. The mean AUC_{∞} ratio of unchanged lenalidomide to the radioactivity in plasma was about 92%, suggesting that the parent compound was the primary radioactive component circulating in plasma. The total recovery of the radioactivity over 10 days averaged approximately 94% of the administered dose, with approximately 90% in urine, 4% in feces, and 0.006% in semen. Two identified metabolites are hydroxy-lenalidomide (pharmacological activity unknown) and N-acetyl-lenalidomide (CC-15656; pharmacologically inactive), with either being less than 5% of the parent in plasma and urine.

No pharmacokinetic or pharmacodynamic interactions were observed between lenalidomide and warfarin; therefore, lenalidomide and warfarin may be co-administered. The effects of lenalidomide on digoxin pharmacokinetics (if any) are small, but a drug interaction cannot be excluded based on the available data.

Proposed Dose and Schedule for Phase 2 Clinical Trials

Lenalidomide doses between 5 mg and 25 mg per day have commonly been used in clinical trials. Because the optimal dose of lenalidomide when given in combination with cediranib is unknown, we will perform a Phase I escalation study. Because lenalidomide 20 mg daily was the mean tolerated dose in the Phase II study of single agent lenalidomide in thyroid cancer,¹⁰ we will start our dose escalation of lenalidomide at 15 mg on 21 days of a 28 day cycle and designate 20 mg daily as the maximal possible dose.

2.3. Rationale

Patients with DTC have few therapeutic options once surgery and RAI have proven ineffective. There are currently no widely accepted standards of care for patients in this setting. Doxorubicin is approved for patients with iodine-refractory thyroid cancer, but response rates are poor and short-lived. There is now mounting clinical data that inhibition of VEGF stimulated angiogenesis has anti-cancer activity. Although cediranib has not been evaluated in thyroid cancer, clinical trials with other VEGFR inhibitors have shown promising results. Likewise, clinical trials with thalidomide and its derivative lenalidomide also show anti-cancer activity. The rationale for combination therapy is to simultaneously target different aberrant pathways implicated in thyroid cancer. We hypothesize that this will limit resistance as seen in single agent therapy and improve response rates.

2.4. Correlative Studies Background

2.4.1. MAPK pathway

RET/PTC rearrangements and *B-RAF* mutations are the most commonly reported molecular aberrations reported in papillary thyroid cancer. *B-RAF* mutations have

been associated with more aggressive iodine-resistant cancers. Additionally, *RAS* mutations have commonly been documented in follicular thyroid cancers. When available, patients enrolled in the phase II study will have archival tumor tissue analyzed for *B-RAF* and *K-RAS* mutations. Testing for these mutations will be done at the University of Chicago.

2.4.2. Plasma

TSH and thyroglobulin measurements will be performed at the respective institution of the enrollee. TSH can stimulate thyroid cancer growth. Participants will have TSH measured pretherapy and every 8 weeks to assess for adequate TSH suppression. Thyroglobulin serves as a tumor marker in thyroid cancer. It is not always reliable because some patients have anti-thyroglobulin antibodies that falsely alter the thyroglobulin measurement and because some advanced cancers lose the ability to make thyroglobulin effectively. However, in patients with cancers that make thyroglobulin, this protein can serve as a useful surrogate of targeted agent activity. Patients who do not have anti-thyroglobulin antibodies will have thyroglobulin measurements pretherapy and at 8 week intervals.

3. PATIENT SELECTION

3.1. Eligibility Criteria

- 3.1.1. Patients must have histologically or cytologically confirmed papillary, follicular, papillary/follicular variant or Hürthle cell carcinoma. Patients must be felt to be poor candidates for or refractory to further surgery or radioactive I-131 therapy. I-131 therapy must have been completed at least 4 weeks prior to enrollment. All patients are expected to be on thyroxine suppression therapy.
- 3.1.2. Patients must have radiographically measurable disease. Radiographically measurable disease is defined as at least one lesion that can be accurately measured in at least one dimension (longest diameter to be recorded) as >20 mm with conventional techniques or as >10 mm with spiral CT scan. Lesions in previously irradiated anatomic areas (external beam radiation) cannot be considered target lesions unless there has been documented growth of those lesions after radiotherapy.
- 3.1.3. Patients must have evidence of disease progression (20% objective growth of existing tumors by RECIST criteria) within the last 12 months.
- 3.1.4. In the Phase I portion, there is no limit on prior systemic therapies (cytotoxic or targeted therapies). However, patients who have discontinued previous VEGF inhibitors secondary to adverse events are not eligible. In the Phase 2 portion,

patients cannot have received more than 1 prior chemotherapy (cytotoxic or targeted) regimen. Prior VEGF-pathway inhibitors or B-RAF inhibitors are permissible.

3.1.5. Although there are data for lenalidomide in pediatric populations,²³ no dosing or adverse event data is currently available on the use of cediranib or cediranib with lenalidomide in patients <18 years of age. Therefore, children are excluded from this study but will be eligible for future pediatric phase II combination trials.

3.1.6. Life expectancy of greater than 12 weeks.

3.1.7. ECOG performance status 0-2 (Karnofsky >60%; see Appendix A).

3.1.8. Patients must have normal organ and marrow function as defined below:

X leukocytes	>3,000/mcL
X absolute neutrophil count	>1,500/mcL
X platelets	>100,000/mcL
X hemoglobin	>9 g/dL
X serum calcium	<12.0 mg/dL
X total serum bilirubin	below or equal to upper limit of institutional normal**
X AST(SGOT)/ALT(SGPT)	≤2.5 X institutional upper limit of normal
X creatinine	below or equal to upper limits of institutional limits

OR

X creatinine clearance	>50 mL/min/1.73 m ² for patients with creatinine levels above institutional normal
------------------------	---

** Patients with hyperbilirubinemia due to Gilbert's syndrome may enroll in the trial.

3.1.9. Patients must have QTc < 480 msec.

3.1.10. The following groups of patients are eligible provided they have New York Heart Association Class II (NYHA; see Appendix G) cardiac function on baseline ECHO/MUGA:

- * those with a history of Class II heart failure who are asymptomatic on treatment
- * those with prior anthracycline exposure
- * those who have received central thoracic radiation that included the heart in the radiotherapy port.

3.1.11. Females of childbearing potential (FCBP)[†] must have a negative serum or urine pregnancy test with a sensitivity of at least 25 mIU/mL within 10 – 14 days prior to and again within 24 hours of starting lenalidomide and must either commit to continued abstinence from heterosexual intercourse or begin TWO acceptable methods of birth control, one highly effective method and one additional effective method AT THE SAME TIME, at least 28 days before she starts taking lenalidomide. FCBP must also agree to ongoing pregnancy testing. Men must agree to use a latex condom during sexual contact with a FCBP even if they have had a successful vasectomy. All patients must be counseled at a minimum of every 28 days about pregnancy precautions and risks of fetal exposure. See Appendix H: Risks of Fetal Exposure, Pregnancy Testing Guidelines and Acceptable Birth Control Methods, AND also Appendix I: Education and Counseling Guidance Document.

[†] A female of childbearing potential is a sexually mature woman who: 1) has not undergone a hysterectomy or bilateral oophorectomy; or 2) has not been naturally postmenopausal for at least 24 consecutive months (i.e., has had menses at any time in the preceding 24 consecutive months).

3.1.12. Females of childbearing potential (FCBP)[†] who receive cediranib alone must also have a negative initial and ongoing pregnancy tests as described above in 3.1.11. FCBP who receive cediranib alone must also commit to continued abstinence from heterosexual intercourse or begin TWO acceptable methods of birth control, one highly effective method and one additional effective method AT THE SAME TIME, at least 28 days before she starts taking cediranib. Men on cediranib alone must agree to use a latex condom during sexual contact with a FCBP even if they have had a successful vasectomy. All patients receiving cediranib alone must be counseled at a minimum of every 28 days about pregnancy precautions and risks of fetal exposure.

3.1.13. Ability to understand and the willingness to sign a written informed consent document.

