11.1.1. Definitions

Evaluable for toxicity. All patients will be evaluable for toxicity from the time of their first treatment with cediranib or cediranib in combination with lenalidomide.

Evaluable for objective response. Only those patients who have measurable disease present at baseline, have received at least one cycle of therapy, and have had their disease re-evaluated will be considered evaluable for response. These patients will have their response classified according to the definitions stated below. (Note: Patients who exhibit objective disease progression prior to the end of cycle 1 will also be considered evaluable.)

Evaluable Non-Target Disease Response. Patients who have lesions present at baseline that are evaluable but do not meet the definitions of measurable disease, have received at least one cycle of therapy, and have had their disease re-evaluated will be considered evaluable for non-target disease. The response assessment is based on the presence, absence, or unequivocal progression of the lesions.

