11.1.2. Disease Parameters

Measurable disease. Measurable lesions are defined as those that can be accurately measured in at least one dimension (longest diameter to be recorded for non-nodal lesions and short axis for nodal lesions) as ≥ 20 mm by chest x-ray, as ≥ 10 mm with CT scan, or ≥ 10 mm with calipers by clinical exam. All tumor measurements must be recorded in millimeters (or decimal fractions of centimeters).

Note: Tumor lesions that are situated in a previously irradiated area are not considered measurable.

Malignant lymph nodes. To be considered pathologically enlarged and measurable, a lymph node must be ≥ 15 mm in short axis when assessed by CT scan (CT scan slice thickness recommended to be no greater than 5 mm). At baseline and in follow-up, only the short axis will be measured and followed.

Non-measurable disease. All other lesions (or sites of disease), including small lesions (longest diameter < 10 mm or pathological lymph nodes with ≥ 10 to < 15 mm short axis), are considered non-measurable disease. Bone lesions, leptomeningeal disease, ascites, pleural/pericardial effusions, lymphangitis cutis/pulmonitis, inflammatory breast disease, and abdominal masses (not followed by CT or MRI), are considered as non-measurable.

Note: Cystic lesions that meet the criteria for radiographically defined simple cysts should

not be considered as malignant lesions (neither measurable nor non-measurable) since they are, by definition, simple cysts.

‘Cystic lesions’ thought to represent cystic metastases can be considered as measurable lesions, if they meet the definition of measurability described above. However, if non-cystic lesions are present in the same patient, these are preferred for selection as target lesions.

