11.1.4. Response Criteria

11.1.4.1. Evaluation of Target Lesions

Complete Response (CR): Disappearance of all target lesions. Any pathological lymph nodes (whether target or non-target) must have reduction in short axis to <10 mm.

Partial Response (PR):	At least a 30% decrease in the sum of the diameters of target lesions, taking as reference the baseline sum diameters
Progressive Disease (PD):	At least a 20% increase in the sum of the diameters of target lesions, taking as reference the smallest sum on study (this includes the baseline sum if that is the smallest on study). In addition to the relative increase of 20%, the sum must also demonstrate an absolute increase of at least 5 mm. (Note: the appearance of one or more new lesions is also considered progressions).
Stable Disease (SD):	Neither sufficient shrinkage to qualify for PR nor sufficient increase to qualify for PD, taking as reference the smallest sum diameters while on study

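### Section 3.1.2 has no lymph-node rule for measurable disease, so a patient whose only qualifying lesions are nodes under 15 mm short axis can meet it and have no target lesion under Section 11.1.2

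*Combined protocol and SAP*

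**What the plan says.** **Eligibility (3.1.2).** The section carries its own definition: "Radiographically measurable disease is defined as at least one lesion that can be accurately measured" in one dimension, with the thresholds set on the longest diameter: "longest diameter to be recorded) as >20 mm with conventional techniques or as >10 mm with spiral CT scan". It does not distinguish nodes from other lesions and does not refer to Section 11.

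**Endpoint assessment (11.1.2).** For a node to be measurable, "a lymph node must be ≥ 15 mm in short axis when assessed by CT scan". The non-measurable class expressly includes "pathological lymph nodes with ≥ 10 to < 15 mm short axis". For nodes, "only the short axis will be measured and followed". Target lesions are chosen from measurable lesions only.

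**Evaluability and response (11.1.1, 11.1.4.3, 13.5.2).** The objective-response set is restricted: "Only those patients who have measurable disease present at baseline", with further conditions. Section 11.1.1 also defines a non-target evaluable group, and 11.1.4.3 gives a table for patients without measurable disease. Its usable outcomes are CR, non-CR/non-PD and PD. Section 13.5.2 assigns every patient to a numbered category: CR, PR, SD, PD, three kinds of early death, or unknown. Categories 4 to 9 count as treatment failure.

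**The concern.** The trial means to enrol patients with measurable disease, and three of its measures depend on a baseline sum of target diameters: partial response, progression by growth of that sum, and percent change in tumour size at the end of cycle 2 (13.4.2). If eligibility uses a looser definition than the endpoint section, some patients can enter without that sum.

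Progression for them would rest on new lesions or on a judgement that non-target disease has unequivocally worsened. Section 11.1.4.2 gives weight to the treating physician's opinion in that judgement, and the trial is open-label. Their response status would also have no clear home in Section 13.5.2. These choices would then be made case by case after data are seen.

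**Working it through.** The plan states no figure on this point to reproduce. The check applies both rules to the same nodes.

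**Step 1. The rules.** Let L be the longest diameter and S the short axis of a node on spiral CT. Section 3.1.2 is met if L > 10 mm. Section 11.1.2 is met if S ≥ 15 mm. The two disagree whenever L > 10 mm and S < 15 mm.

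| Node, L x S (mm) | 3.1.2 met | Measurable under 11.1.2 |
|---|---|---|
| 14 x 11 | yes | no |
| 18 x 12 | yes | no |
| 22 x 14.9 | yes | no |
| 16 x 15 | yes | yes |
| 20 x 16 | yes | yes |

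None of this depends on whether the 10 and 20 mm limits are inclusive.

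**Step 2. Does 3.1.3 close the gap?** It requires 20% growth within 12 months by RECIST but names no version. Take the 18 x 12 mm node. Read on longest diameter, as in 3.1.2, growth from 18 / 1.20 = 15 mm is enough. Read by 11.1.4.1, the 20% applies to a target sum, which this patient lacks, and an absolute rise of 5 mm is also needed, whereas 18 − 15 = 3 mm. So 3.1.3 may exclude some of these patients, depending on the version intended.

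**Step 3. What follows with no target lesion.**
- Partial response is defined on the target sum (11.1.4.1), and the non-target table has no such row.
- Progression by 20% and 5 mm needs the sum and cannot be applied.
- Percent change to the end of cycle 2 has no baseline value. The 13.4.2 scoring for new lesions, 1.2 times the larger of the pre- and post-treatment sums, has nothing to work on.
- CR and PD remain available through the non-target table.
- Non-CR/non-PD has no entry in 13.5.2. Calling it SD goes against the footnote to the 11.1.4.3 table. Calling it unknown places it in category 9, which counts as failure.

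**Step 4. A second mismatch in the same two sections.** Section 3.1.2 lets a lesion in an irradiated area be a target after documented growth. A note in 11.1.2 says lesions in such areas are not measurable, with no exception.

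**The case against.** The strongest reply is that the protocol already provides for these patients. Section 11.1.1 has a non-target evaluable group, 11.1.4.3 has a table for them, and PFS (11.1.6) still counts progression and death from any cause. Section 11.1.4.2 asks for later confirmation of non-target-only progression, and 3.1.3 removes some candidates. All of that stands and limits the consequences. It does not make the two definitions agree, and it leaves non-CR/non-PD unmapped in 13.5.2.

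A reader might infer more than the documents support:

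- **That patients with nodal disease in general lack targets.** Only those whose sole qualifying lesions are such nodes are affected. One measurable non-nodal lesion, or one node of at least 15 mm short axis, supplies a target.
- **That a 12 x 8 mm node qualifies although it already meets the nodal CR condition.** That condition says such nodes "must have reduction in short axis to <10 mm". But 11.1.4.2 treats nodes below that size as non-pathological, so such a node is doubtful as the sole evidence of disease. The point does not rest on it.
- **That progression will be recorded later, or that PFS is biased.** No text shows a delay. Both arms are randomised under one eligibility rule, so no difference between arms is shown.
- **That all these patients count as non-responders.** CR remains possible, although PR does not.
- **That the dilution of the response rate can be stated.** Any figure needs an assumed share. If 5% to 15% of the 110 Phase II patients were affected, that is 5.5 to 16.5 patients. With no CR among them, a 30% response rate in the others would become 0.30 x 0.95 = 28.5% to 0.30 x 0.85 = 25.5%. A 14% rate would become 0.14 x 0.95 = 13.3% to 0.14 x 0.85 = 11.9%. The 30% and 14% are the axitinib and motesanib rates in Section 2.1. The share is purely an assumption, so these are illustrations and not estimates.

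**Conclusion.** The inconsistency is real and lies in current text. On its own words, 3.1.2 admits patients whom 11.1.2 would call non-measurable when their only qualifying lesions are nodes longer than 10 mm with a short axis under 15 mm. For them, PR, the 20%/5 mm rule and the cycle-2 tumour-size measure cannot be applied, and 13.5.2 does not say where non-CR/non-PD goes.

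The reach is limited. PFS remains defined, no bias between arms is shown, and the number of patients cannot be derived from the documents. The effect on the primary endpoint is confined to how progression is determined in this subgroup. The direct loss falls on response and early tumour size, both secondary. Confidence is high on the mismatch; the size of its effect is unknown.

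**What to change.** Replace the definition in 3.1.2 with a reference to 11.1.2, for example: *Measurable disease is defined as in Section 11.1.2: at least one non-nodal lesion of at least 10 mm longest diameter on CT or at least 20 mm on chest x-ray, or a lymph node of at least 15 mm short axis on CT.* State in 3.1.3 which RECIST version applies.

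In the same edit, reconcile the irradiated-lesion sentence of 3.1.2 with the contrary note in 11.1.2. Otherwise the new reference would move that conflict inside 3.1.2.

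For patients already enrolled without an 11.1.2-measurable lesion, add to Section 13:
- response and progression are assessed under the non-target table in 11.1.4.3;
- a stated rule maps non-CR/non-PD to a 13.5.2 category;
- these patients are left out of the tumour-size comparison, with their number reported by arm.

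If accrual has ended, which the documents do not say, only this analysis part still has effect. It should be fixed before the data are analysed.

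The cost is a short amendment with no new scans. The downside is that a few patients with only small nodes become ineligible.

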3.2. Exclusion Criteria

3.2.1. Patients who have had chemotherapy or radiotherapy within 4 weeks (6 weeks for nitrosoureas or mitomycin C) prior to entering the study or those who have not recovered from adverse events due to agents administered more than 4 weeks earlier. At least 4 weeks must have elapsed since any major surgery. Patients with prior use of thalidomide or lenalidomide are excluded.

3.2.2. Patients may not be receiving any other investigational agents.

3.2.3. Patients with known brain metastases should be excluded because of their poor prognosis and because they often develop progressive neurologic

dysfunction that would confound the evaluation of neurologic and other adverse events. N.B.: Patients with brain metastases with stable neurologic status following local therapy (surgery or radiation) for at least 8 weeks from definitive therapy and without neurologic dysfunction that would confound the evaluation of neurologic and other adverse events are eligible for participation.

- 3.2.4. History of allergic reactions attributed to compounds of similar chemical or biologic composition to cediranib or lenalidomide or other agents used in the study.
- 3.2.5. Patients with poorly controlled hypertension (systolic blood pressure of 140 mmHg or higher or diastolic blood pressure of 90 mmHg or higher) are ineligible.
- 3.2.6. Patients with 1+ proteinuria or greater on urinalysis should collect a 24 hour urine collection. Patients with greater than 1.5 gram protein/ 24 hours are excluded.
- 3.2.7. Because lenalidomide may increase the risk of DVT or PE, patients must stop Epopen at least 4 weeks prior to enrollment.
- 3.2.8. Patients with any condition (e.g., gastrointestinal tract disease resulting in malabsorption, prior surgical procedures affecting absorption, or active peptic ulcer disease) that impairs their ability to absorb cediranib tablets or lenalidomide capsules are excluded. However, for patients who are unable to swallow cediranib tablets, cediranib tablets may be administered as a dispersion in water (ie, either drinking water, sterile water [for injection] or purified water). Cediranib can be administered via nasogastric tube or gastostomy tube. See section 5.1 for recommended procedure. For patients unable to swallow lenalidomide whole, lenalidomide can be administered via gastostomy feeding tube following the instructions in Appendix M.
- 3.2.9. Patients with any of the following conditions are excluded:
- Serious or non-healing wound, ulcer, or bone fracture.
 - History of abdominal fistula, gastrointestinal perforation, or intra-abdominal abscess within 28 days of treatment.
 - Any history of cerebrovascular accident (CVA) or transient ischemic attack within 12 months prior to study entry.
 - History of myocardial infarction, cardiac arrhythmia, stable/unstable angina, symptomatic congestive heart failure, or coronary/peripheral artery bypass graft or stenting within 12 months prior to study entry.
 - History of pulmonary embolism within the past 12 months.
 - Class III or IV heart failure as defined by the NYHA functional classification system (see Appendix G).

- 3.2.10. Patients with uncontrolled intercurrent illness including, but not limited to, ongoing or active infections or psychiatric illness/social situations that would limit compliance with study requirements are ineligible.
- 3.2.11. Pregnant women are excluded from this study because cediranib and lenalidomide are agents with the potential for teratogenic or abortifacient effects. Because there is an unknown but potential risk for adverse events in nursing infants secondary to treatment of the mother with cediranib or lenalidomide, breastfeeding should be discontinued if the mother is treated with cediranib with or without lenalidomide.
- 3.2.12. HIV-positive patients on combination antiretroviral therapy are ineligible because of the potential for pharmacokinetic interactions with cediranib or cediranib with lenalidomide. In addition, these patients are at increased risk of lethal infections when treated with marrow-suppressive therapy. Appropriate studies will be undertaken in patients receiving combination antiretroviral therapy when indicated.

